6.4 Non-relapse Mortality

The population for the analysis of NRM will be all participants who are randomly assigned to receive either Shared Care or Usual Care based on an intent-to-treat principle (n=324), meaning that the patients will be analyzed according to their randomly assigned treatment, regardless of how they may have actually been treated. The primary hypothesis of this aim is that HCT-related clinical outcomes will not be compromised in the Shared Care group (i.e., non-inferiority test). Causes of death after allogeneic HCT can be due to relapse of the primary diagnosis, but also due to causes other than the disease itself such as infection, GVHD, or organ failure which are termed “non-relapse mortality (NRM).” **100-day NRM** will be the primary outcome, as it is most sensitive to quality of post-HCT care. Other endpoints in this aim include overall survival, progression-free survival, relapse, emergency room admissions, infections, and GVHD. Between 2012 and 2015, the 100-day NRM rate at DFCI was 2-3%. Based on this information, the

Version 8 , 11/16/2020

hypothesis of testing non-inferiority of Shared Care is defined such that the difference in 100-day NRM rate is not greater than a non-inferiority margin of 5%, that is:

$$H_0: P_s - P_u \geq 0.05; H_a: P_s - P_u < 0.05$$

where H_0 and H_a denote the null and alternative hypothesis, respectively, P_s denotes the 100-day NRM rate in the Shared Care group and P_u denotes the rate in the Usual Care group. For example, if the 100-day NRM rate is 2% in the Usual Care group and 3% in the Shared Care group, there will be 85% power of rejecting the null hypothesis of inferiority at one-sided type I error rate of 0.1 (Figure 2). If, however, the 100-day NRM is 3% in the Usual Care and 3.7% in the Shared Care group, there will be 81% power of rejecting the null hypothesis of inferiority. This power calculation is based on a Pearson chi-square test for two proportions using PROC POWER in SAS v9.2. Finally, when the study reaches 50% of its accrual ($n=162$) and the last patient in this set is followed for 100 days, we will perform an analysis of 100-day NRM to ensure the difference in the 100-day NRM rate is within a 5% non-inferiority margin (an “interim look.”) If the 100-day NRM rate in Shared Care is $> 5\%$ higher than that in Usual Care, accrual will be halted pending review by the Data Safety Monitoring Board. The DSMB may recommend permanent closure of enrollment or continuation of the study. Of note, there may be a small attrition in type I error rate due to the interim look, which is not incorporated in the above error rate of 0.1.

The data analysis will be based on the intent-to-treat principle. The 100-day NRM will be analyzed as a binary outcome as well as in the competing risks framework

treating relapse as a competing event, with the latter being the primary analysis. In the competing risks data analysis, we will examine whether the competing event of relapse is similar between the two types of care. Other endpoints in this aim include overall survival, progression-free survival, NRM, relapse, and a/c GVHD. For overall and progression-free survival, standard survival analysis will be performed, including the Kaplan-Meier method for estimation of survival functions, log-rank test for comparison of KM curves, and Cox proportional hazards model for multivariable regression analysis. For NRM, relapse and a/c GVHD, competing risks data analysis will be performed. Since these endpoints are immunologically intertwined, it is critical to analyze them in a competing risks framework.^{20,21} In addition, we will perform a sensitivity analysis comparing baseline characteristics and clinical outcomes between the Shared Care and the non-randomized usual care group, and between the randomized Usual Care group and the non-randomized usual care group. Again, we anticipate no missing data in HCT clinical outcomes since reporting of HCT-related outcomes data to the CIBMTR is mandatory

Table 4. Pre-specified Attributes to Examine Heterogeneity

Patient attribute	Age Patient sex CMV seropositive status
Donor attribute	Donor sex Donor type: related vs. unrelated HLA type: matched vs. mismatched CMV seropositive status
Disease attribute	Blood Cancer Diagnosis Disease status
Transplant attribute	Conditioning intensity GVHD prophylaxis Graft source

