5.0 STUDY DESIGNS AND METHODS

5.1 DESIGN/ STUDY TYPE

We propose a randomized control trial with two arms. Participants will be randomized 1:1 to the intervention arm (Shared Care) or to the conventional arm (Usual Care). Randomization will be stratified by site and conditioning intensity (Full vs Reduced intensity).

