5.6 ADVERSE REACTION AND THEIR MANAGEMENT

A potential area of concern is that there may not be continuous communication among patients, DFCI transplant providers, and local providers. For this reason we have created the ACT.md web tool for providers to communicate with each other in real time and for patients to directly observe – and potentially add to – this communication (see section 5.52).

The non-randomized cohort of patients will receive Usual Care following their HCT procedure. They will be subject to the same medical record reviews and surveys in the Usual Care arm.

The consent forms outline the risks associated with participation. The risks to both the randomized and non randomized cohorts are expected to be minimal and all attempts will be made to minimize any anticipated issues with communication. If a patient declines

Version 8 , 11/16/2020

randomization and collection of outcomes, then the patient declines complete participation, s/he will not sign informed consent, will not be in this research study and no data will be collected.

The coordinating center (Dana-Farber) will take several steps to protect against and to minimize risks to privacy of individuals and confidentiality of data:

1. All data analyses will be conducted at Dana-Farber under the direct supervision of the PI.
2. Once the data are received, all study data will be stored on a password-protected RedCap database.

Data will be used for research purposes only. At no time will any patient be individually identified in the final analyses. We are confident that the steps outlined above will effectively protect against this risk.

Estimated study population characteristics are presented in Table 3, which are derived from our recent survey of patients at 180 days after HCT (in the table, autologous patients are excluded).^{4,11,12} The response rate we achieved (72%) provides insight into the high level of engagement of HCT patients and caregivers, even when concerning difficult topics such as personal finances.

Finally, to address study risk of missed tasks and miscommunication, we have planned interim analyses to determine if there are worse HCT-related outcomes for Shared Care patients; if so, the study will be stopped immediately and patients returned to usual care.

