Responses may be returned on the written query or on an amended paper case report form, or in the case of electronic queries, within the electronic data capture (eDC) system. In the case of a written query for data submitted on a paper case report form, the query must be attached to the specific data being re-submitted in response.

If study forms are not submitted on schedule, the Participating Institution will periodically receive a Missing Form Report from the Coordinating Center noting the missing forms.

MONITORING: QUALITY CONTROL

The quality control process for a clinical trial requires verification of protocol compliance and data accuracy. The Coordinating Center, with the aid of the DF/HCC Office of Data Quality, provides quality control oversight for the protocol.

Ongoing Monitoring of Protocol Compliance

Meetings will be held at least twice each year, which will mean at least eight reviews during the proposed Shared Care study period. Each protocol is discussed in both an open and a closed session. In the open session, members of the study team, including the study statistician [name] and the PI, [name], may be present to review the conduct of the trial and to answer questions from members of the DSMB. The focus of this open session will

be on accrual, protocol compliance, and general toxicity issues. Outcomes will normally not be discussed during the open session. The closed session of the DSMB will include only the voting, non-voting, and ad hoc members, and will include discussion of the general conduct of the trial and outcomes, including non-relapsed mortality. The study statistician may be asked to present outcome data during the closed session.

The DSMB will review interim analyses of outcomes (prepared by the lead statistician) and make recommendations as to whether the study needs to be continued, changed or terminated. Site adverse event reports will be submitted to the Statistical Coordinating Center at Dana-Farber. If such an event occurs, three entities (SCIG; site IRB; SC-PAP and the DF/HCC DSMB) will convene to determine if it is safe for the subject to remain on study, if the study is safe to continue, if all subjects need to be notified, and if any changes to the protocol are warranted.

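### The n=162 interim look cannot ensure that excess 100-day NRM is within 5 points: its raw trigger misses a true 5-point excess roughly half the time, and no other outcome has a defined interim analysis

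*Combined protocol and SAP*

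**What the plan says.** Section 6.4 defines one interim look. It takes place when 162 of 324 patients have been accrued "and the last patient in this set is followed for 100 days". Its purpose is given as: "we will perform an analysis of 100-day NRM to ensure the difference in the 100-day NRM rate is within a 5% non-inferiority margin". Accrual is halted, pending DSMB review, if the observed Shared Care rate is more than 5 points above Usual Care, and the DSMB may then recommend closing enrolment or continuing. No confidence limit, test or detection probability accompanies the trigger.

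Section 5.6 addresses the risk of missed tasks and miscommunication by saying "we have planned interim analyses to determine if there are worse HCT-related outcomes for Shared Care patients". Section 5.61 repeats this. Both say that if outcomes are worse the study stops at once and patients go back to usual care.

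The clinical endpoints under 6.4 go beyond NRM: "Other endpoints in this aim include overall survival, progression-free survival, relapse, emergency room admissions, infections, and GVHD".

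The Data and Safety Monitoring Plan (Ongoing Monitoring of Protocol Compliance) adds DSMB oversight: "Meetings will be held at least twice each year, which will mean at least eight reviews during the proposed Shared Care study period". Closed sessions discuss outcomes, with NRM the only one named. The DSMB reviews interim analyses prepared by the lead statistician and may recommend termination. No further endpoint and no threshold is given for these reviews.

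**The concern.** A threshold placed on a point estimate does not bound the true difference. At 2-3% NRM, about two deaths per arm are expected by the interim look, so one or two deaths decide whether the trigger fires. Staying below it is weak evidence that the excess is inside the margin, yet the protocol's wording tells the DSMB and the IRB that the look secures exactly that.

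The second issue is coverage. The harms that 5.6 has in mind could appear as infections, GVHD, emergency room admissions or deaths after relapse before they move 100-day NRM. None of these has a defined interim analysis.

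At stake is whether an arm at or beyond the unacceptable margin could recruit to completion after a check that is described as excluding this.

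**Working it through.** **Inputs.** From section 6.4: 324 randomised, interim at 162, control 100-day NRM 2-3%, margin 0.05, one-sided alpha 0.10, trigger at an observed difference above 0.05. From section 5.1: 1:1 allocation, stratified by site and conditioning intensity. Assumption: 81 per arm at the look. The plan gives no block size, so nearby splits are checked too.

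**The plan's own figures first.** Power = Φ((0.05 − (Ps − Pu))/SE − 1.282), with SE = √[Pu(1−Pu)/162 + Ps(1−Ps)/162].

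- 2% vs 3%: SE = 0.01734; 0.04/0.01734 − 1.282 = 1.025; power 84.7% (stated 85%).
- 3% vs 3.7%: SE = 0.01999; 0.043/0.01999 − 1.282 = 0.870; power 80.8% (stated 81%).

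The final-analysis inputs therefore reproduce. The plan states no operating characteristic for the interim look, so there is no interim figure to reproduce.

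**What the trigger needs.** 4/81 = 4.9% does not halt; 5/81 = 6.2% does. At 81/81 the rule needs at least five more NRM deaths in Shared Care. Expected deaths in an arm at the control rate are 81 × 0.02 = 1.6 to 81 × 0.03 = 2.4.

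**Probability of missing a true excess.** Exact sum over independent binomials of P(Xs/ns − Xu/nu ≤ 0.05), with control NRM from 2% to 3%:

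| Shared/Usual split | True excess 5 points | True excess 7 points |
|---|---|---|
| 81/81 | 57.1-58.0% | 34.9-35.9% |
| 82/80 | 55.6-56.7% | 33.5-34.3% |
| 83/79 | 54.1-55.3% | 32.2-32.8% |
| 84/78 | 52.5-54.0% | 30.9-31.4% |
| 80/82 | 45.6-47.0% | 25.3-26.1% |
| 79/83 | 45.4-46.1% | 24.9-27.0% |
| 78/84 | 46.8-47.7% | 26.1-28.4% |

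A simulation of 1,000,000 draws at 81/81 agrees (58.0% and 57.1% missed at 5 points). Detection at the margin is therefore about 42-55%. The drop between 81/81 and 80/82 is discreteness: with 80 in Shared Care, an excess of four deaths such as 6 vs 2 gives 6/80 − 2/82 = 5.06%, which now triggers.

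At 81/81, a 10-point excess is missed 13-14% of the time. With no true difference the trigger fires 0.7-1.9% of the time.

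**What a non-halting result can hide.** Take 6 vs 2 deaths at 81/81. The difference is 4/81 = 0.0494. SE = √[(0.0741 × 0.9259 + 0.0247 × 0.9753)/81] = 0.0338. The one-sided 90% upper bound (Wald) is 0.0494 + 1.282 × 0.0338 = 0.093, or 9.3 points against a margin of 5.

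**Coverage, side by side.**

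| Source | Endpoint | Timing | Threshold | Consequence |
|---|---|---|---|---|
| 6.4 | 100-day NRM only | n=162 plus 100 days | observed difference >5 points | accrual halted; DSMB may recommend closure or continuation |
| 5.6, 5.61 | HCT-related outcomes | not given | not given | study stopped at once; patients return to usual care |
| Monitoring plan | outcomes, NRM the only one named | at least twice a year | not given | DSMB recommends continue, change or terminate |

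**The case against.** Four points on the other side deserve weight.

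**The miss rate is partly built in.** Any point-estimate trigger misses about half the time when the truth sits on its threshold. A reader might infer from the 57-58% figure that an arm at the margin passes more often than not. That holds at 81/81 and when Shared Care is slightly larger, but not when it is slightly smaller, and stratified randomisation with no stated block size does not guarantee 81/81. Roughly half is the supportable statement. It still contradicts the stated purpose, and the 25-36% miss at 7 points lies beyond the threshold.

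**The look does not stand alone.** A reader might infer that this is the trial's only safety check, or that 5.6 rests on it. The documents do not support either. The monitoring plan provides at least eight DSMB reviews, with outcome data and power to recommend termination. Sections 5.6 and 5.61 speak of interim analyses in the plural and do not cite the 6.4 look. What remains is narrower: only the 6.4 look has a stated endpoint, timing and threshold.

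**The choice of NRM is reasoned.** Section 6.4 calls it the outcome most sensitive to the quality of post-transplant care. That justifies it as the primary outcome, but does not supply the wider interim reading that 5.6 and 5.61 describe.

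**Passing the look is not the non-inferiority conclusion.** That comes from the final test at n=324. In simulation with a true 5-point excess at 81/81 (one-sided 0.10, Wald), only about 11-12% of trials both pass the look and go on to meet non-inferiority. A reader who infers that the protocol would accept a passed look as proof of safety goes too far. The point concerns protection of patients during accrual and an accurate description of the look.

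**Conclusion.** The point holds in this form. The n=162 rule cannot do what 6.4 says it is for. It detects a true 5-point excess in 100-day NRM with probability about 42-55%, misses a 7-point excess about 25-36% of the time, and lets through results whose one-sided 90% upper bound is nearly twice the margin. It concerns 100-day NRM, not mortality in general: deaths after relapse or after day 100 are outside the look.

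It is the only interim analysis with a full rule, and it reads one endpoint where 5.6 and 5.61 promise a broader reading. Those sections and 6.4 also give different consequences, which must be reconciled.

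The figures assume splits between 78/84 and 84/78, a control rate of 2-3% and complete 100-day follow-up. This should be corrected; it does not undermine the final analysis.

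**What to change.** 1. In 6.4, replace the claim that the look ensures the difference is within the margin with a statement that it screens for a large excess. State its detection probability at the margin (about 42-55%, depending on the split). Give the DSMB the one-sided 90% upper bound, which matches the plan's own alpha, beside the raw difference.
2. Add by-arm all-cause death, relapse, GVHD, infections and emergency room admissions to this look and to the closed DSMB reports. They correspond to endpoints already listed in 6.4, and this brings 6.4 and the monitoring plan into line with 5.6 and 5.61.
3. Reconcile 5.6 and 5.61 with 6.4 on what follows an adverse interim finding.

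Lowering the trigger to an excess of four deaths is tempting but not recommended. At 81/81 detection at the margin rises only to 57%, so about 43% are still missed. At 79/83 it gains nothing, because four excess deaths already trigger there. It also sits below the plan's margin (4/81 = 4.9%), and a fixed count ignores unequal arms.

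The cost is protocol wording, a few extra DSMB tables and a less favourable description of the look. No extra patients are needed.

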6.5 HETEROGENEITY IN TREATMENT (HTE) EFFECTS

Heterogeneity of the group effect (Shared Care vs. Usual Care) on outcomes will be examined for pre-specified patient, donor, disease and transplant related attributes (Table 4). The attributes

Version 8 , 11/16/2020

shown are known risk factors for allogeneic HCT. Since this is a randomized study, we anticipate that all these attributes will be well balanced between two groups. With respect to patient gender and ethnicity, we are aware of no data that would lead us to expect differential effects of treatments in allogeneic HCT by gender and ethnicity. However, when the proposed study is completed, we will perform a multivariable linear regression analysis on FACT-BMT and PSS-4 including attributes shown in Table 4 and type of care (Shared vs. Usual) to identify factors associated with a better outcome. In addition, we will test interactions between each group (Shared vs. Usual) and attributes. If any of these attributes perform better in one group over the other, we will report the results to facilitate further investigation in future studies.

- 8th grade or less
- Some high school, but did not graduate
- High school graduate or GED
- Some college or Associate degree
- Bachelor degree
- Graduate degree

4. Do you consider yourself Hispanic or Latino?

- Yes, Hispanic or Latino
- No, not Hispanic or Latino

5. What is your race? Please mark one or more.

- White
- Black or African-American
- Asian
- Native Hawaiian or Pacific Islander
- American Indian or Alaskan Native
- More than one race

6. What is your current marital status?

- Married
- Widowed
- Divorced

Version 8 , 11/16/2020

- Separated
- Never married

7. What is your current employment status?

- Not employed (including retired, student or homemaker)
- Unemployed and looking for work
- Taking a leave of absence, but still have a job
- Working full or part-time (if self-employed, also check here)

8. What is your current occupation, or if not currently working, what was your last job for pay?

Please specify occupation: _____

Employment

9. In the week of your transplant, what was your employment status?

- Not employed (including retired, student or homemaker) → **If not employed, go to #17**
- Unemployed and looking for work → **If unemployed, go to #17**
- Taking a leave of absence or time off, but still had a job
- Working full or part-time (if self-employed, also check here)

10. What was your job for pay during the week of your transplant?

Please specify occupation: _____

11. What was your monthly income from employment at that time?

- Less than \$1,000
- \$1,000 to \$2,999
- \$3,000 to \$4,999
- \$5,000 to \$6,999
- \$7,000 or more

12. Since your transplant, how supportive has your employer been about you returning to work? Please circle one.

Unsupportive					Completely Supportive	Not Applicable
1	2	3	4	5		NA

13. Since your transplant, were you able to use family and medical leave (FMLA) provided

through your employer?

- Yes
- No, not offered by employer
- No, did not need it
- No, self-employed or not employed

14. Since your transplant, have you used any of the following? Please mark yes or no for each.

- Vacation time..... Yes No
- Employer paid sick days or paid medical leave..... Yes No
- Personally purchased or employer-sponsored disability insurance..... Yes No
- Unpaid time off..... Yes No

15. Since your transplant, about how much total time have you taken off from work?

Write in number of weeks: _____

16. Since your transplant, how much of the time you took off was paid time off?

- None
- Less than half
- About half
- More than half
- All

Current Household Finances

17. In general, how satisfied are you with your family’s present financial situation? Please circle one.

Not satisfied at all Completely satisfied

1 2 3 4 5

18. How difficult is it for you/your family to meet monthly payments on your bills? Please circle one.

Not difficult at all Extremely difficult

1 2 3 4 5

19. How do your family’s finances usually work out at the end of the month?

Version 8 , 11/16/2020

- Some money left over
- Just enough money
- Not enough money

20. Compared to before your transplant, how has your monthly household income changed?

- It has decreased
- It is about the same
- It has increased

21. The following questions ask about things people do when money is tight. Since your transplant, how often did you or your family have to do any of the following? Please circle one.

	Never	Rarely	Sometimes	Often
Reduce spending on essential household expenses (food, clothing, rent/mortgage)?.....	1	2	3	4
Withdraw from retirement or savings accounts?...	1	2	3	4
Borrow money to help pay for bills?.....	1	2	3	4
Reduce leisure activities?.....	1	2	3	4
Cut back on prescribed medications?.....	1	2	3	4

22. Since your transplant, have you received any of the following resources to help cover expenses? Please check all that apply.

- Social Security Disability Insurance or Social Security Insurance
- Government assistance programs (food stamps, fuel or cash assistance)
- Dana-Farber financial assistance (discount hotel rooms, gas or food gift cards)
- Local or national charities (churches/synagogues, American Cancer Society)
- None of the above

23. What is your current monthly household income (include income from all household members)?

- Less than \$1,000
- \$1,000 to \$2,999
- \$3,000 to \$4,999
- \$5,000 to \$6,999
- \$7,000 or more

Health Insurance and Medical Costs

24. How satisfied are you with your current insurance coverage? Please circle one.

Not satisfied at All

Completely satisfied

1 2 3 4 5

25. About how much of your own money did you spend last month for your medical care (including prescriptions, co-payments, deductibles, and premiums)?

\$ _____ dollars per month

26. The next questions are about costs associated with your transplant that are not direct medical costs. Since your transplant, how difficult has it been for you to pay for the following costs? Please circle one number or “N/A” if you did not have the type of cost after your transplant.

	Not at all difficult				Extremely difficult	Not Applicable
Paying to temporarily relocate closer to transplant center.....	1	2	3	4	5	N/A
Paying for transportation to and from your appointments (gas, parking).....	1	2	3	4	5	N/A
Paying for transplant-related changes at home (cleaning, special foods).....	1	2	3	4	5	N/A
Paying for care services for children or parents usually in my care.....	1	2	3	4	5	N/A

27. How difficult is it for you to pay your medical bills (including prescriptions, co-payments, premiums, and deductibles)? Please circle one.

Not difficult at all

Extremely difficult

1 2 3 4 5

28. The following questions ask about things that may make your life more difficult or stressful.

During the last month, how much have each of the following added stress in your life?

	Not at all			A lot
Worry about being a burden on your family...	1	2	3	4
Worry about not having money for necessities like food, utilities, and housing.....	1	2	3	4
Worry about losing or not having health insurance.....	1	2	3	4
Worry about cost of your health insurance.....	1	2	3	4
Worry about paying medical bills.....	1	2	3	4

29. Thinking back to before your transplant, how informed do you feel you were about post-transplant related costs?

- Not at all informed
- Somewhat informed
- Extremely informed

30. Who gave you information about post-transplant related costs? (Check all that apply)

- Doctor
- Nurse
- Social worker
- Resource specialist
- Someone else → Who? _____
- No one

C. Caregiver Quality of Life – Adapted Patient Survey

100 days post transplant:

Which of the following statements best describes your relationship with your primary caregiver?

- My caregiver is a family member.
- My caregiver is a friend.
- My caregiver is a paid professional.
- My caregiver is other _____

Below is a list of statements that people caring for loved ones with cancer have said are important. By circling one number per line, please indicate how true each statement has been for you during the past 7 days.

0 = Not at all **1** = A little bit **2** = Somewhat **3** = Quite a bit **4** = Very much

My caregiver seems...

1. ...supported by friends and neighbors	0	1	2	3	4
2. ...to have adequate information about my care	0	1	2	3	4
3. ...to have a new daily routine since my transplant	0	1	2	3	4
4. ...more tired than before my transplant	0	1	2	3	4
5. ...more stressed than before my transplant	0	1	2	3	4

I feel that...

6. ...my caregiver is part of my decision-making team regarding my transplant	0	1	2	3	4
7. ...my caregiver and I have developed a closer relationship since transplant	0	1	2	3	4
8. ...the transplant process has negatively impacted my relationship with my caregiver	0	1	2	3	4
9. ...I am dependent on my caregiver for transportation	0	1	2	3	4
10. ...my caregiver takes primary responsibility for my diet	0	1	2	3	4

Circle the answer below that best describes the employment situation of your caregiver:

My caregiver...

- a. was not working before and is not working now
- b. was not working before and is working now
- c. was working before and is not working now
- d. was working before and is working now

Version 8 , 11/16/2020

180 days post transplant:

Has your primary caregiver changed since you last filled out this survey (at 100 days post-transplant)?

- Yes, I have a different caregiver.
- No, my caregiver has remained the same.
- I do not remember.

Which of the following statements best describes your relationship with your primary caregiver?

- My caregiver is a family member.
- My caregiver is a friend.
- My caregiver is a paid professional.
- My caregiver is other _____

Below is a list of statements that people caring for loved ones with cancer have said are important. By circling one number per line, please indicate how true each statement has been for you during the past 7 days.

0 = Not at all **1** = A little bit **2** = Somewhat **3** = Quite a bit **4** = Very much

My caregiver seems...

1...supported by friends and neighbors	0	1	2	3	4
2...to have adequate information about my care	0	1	2	3	4
3...to have a new daily routine since my transplant	0	1	2	3	4
4...more tired than before my transplant	0	1	2	3	4
5...more stressed than before my transplant	0	1	2	3	4

I feel that...

6...my caregiver is part of my decision-making team regarding my transplant	0	1	2	3	4
7...my caregiver and I have developed a closer relationship since transplant	0	1	2	3	4
8...the transplant process has negatively impacted my relationship with my caregiver	0	1	2	3	4
9...I am dependent on my caregiver for transportation	0	1	2	3	4
10...my caregiver takes primary responsibility for my diet	0	1	2	3	4

Circle the answer below that best describes the employment situation of your caregiver:

My caregiver...

- a. was not working before and is not working now
- b. was not working before and is working now
- c. was working before and is not working now
- d. was working before and is working now

Version 8 , 11/16/2020

D. European Organisation for Research and Treatment of Cancer (EORTC QLQ-C30)

EORTC QLQ-C30 (version 3)

We are interested in some things about you and your health. Please answer all of the questions yourself by circling the number that best applies to you. There are no "right" or "wrong" answers. The information that you provide will remain strictly confidential.

Please fill in your initials:

Your birthdate (Day, Month, Year):

Today's date (Day, Month, Year): 31

Not at A Quite Very

All (1) Little (2) a Bit (3) Much (4)

1. Do you have any trouble doing strenuous activities, like carrying a heavy shopping bag or a suitcase?	1	2	3	4
2. Do you have any trouble taking a long walk?	1	2	3	4
3. Do you have any trouble taking a short walk outside of the house?	1	2	3	4
4. Do you need to stay in bed or a chair during the day?	1	2	3	4
5. Do you need help with eating, dressing, washing yourself or using the toilet?	1	2	3	4

During the past week: Not at A Quite Very

All (1) Little (2) a Bit (3) Much (4)

6. Were you limited in doing either your work or other daily activities?	1	2	3	4
7. Were you limited in pursuing your hobbies or other leisure time activities?	1	2	3	4
8. Were you short of breath?	1	2	3	4
9. Have you had pain?	1	2	3	4
10. Did you need to rest?	1	2	3	4
11. Have you had trouble sleeping?	1	2	3	4
12. Have you felt weak?	1	2	3	4
13. Have you lacked appetite?	1	2	3	4
14. Have you felt nauseated?	1	2	3	4
15. Have you vomited?	1	2	3	4
16. Have you been constipated?	1	2	3	4

Please go on to the next page

During the past week: Not at A Quite Very

All (1) Little (2) a Bit (3) Much (4)

17. Have you had diarrhea?	1	2	3	4
18. Were you tired?	1	2	3	4
19. Did pain interfere with your daily activities?	1	2	3	4
20. Have you had difficulty in concentrating on things, like reading a newspaper or watching television?	1	2	3	4
21. Did you feel tense?	1	2	3	4
22. Did you worry?	1	2	3	4
23. Did you feel irritable?	1	2	3	4
24. Did you feel depressed?	1	2	3	4
25. Have you had difficulty remembering things?	1	2	3	4
26. Has your physical condition or medical treatment interfered with your family life?	1	2	3	4
27. Has your physical condition or medical treatment interfered with your social activities?	1	2	3	4
28. Has your physical condition or medical treatment caused you financial difficulties?	1	2	3	4

For the following questions please circle the number between 1 and 7 that best applies to you

29. How would you rate your overall health during the past week?
 Very poor 1 2 3 4 5 6 7 Excellent

30. How would you rate your overall quality of life during the past week?
 Very poor 1 2 3 4 5 6 7 Excellent

E. FACT-BMT

FACT-BMT (Version 4)

Below is a list of statements that other people with your illness have said are important. Please circle or mark one number per line to indicate your response as it applies to the past 7 days.

PHYSICAL WELL-BEING		Not at all	A little bit	Some- what	Quite a bit	Very much
GP1	I have a lack of energy	0	1	2	3	4
GP2	I have nausea	0	1	2	3	4
GP3	Because of my physical condition, I have trouble meeting the needs of my family	0	1	2	3	4
GP4	I have pain	0	1	2	3	4
GP5	I am bothered by side effects of treatment	0	1	2	3	4
GP6	I feel ill	0	1	2	3	4
GP7	I am forced to spend time in bed	0	1	2	3	4

SOCIAL/FAMILY WELL-BEING		Not at all	A little bit	Some- what	Quite a bit	Very much
G81	I feel close to my friends	0	1	2	3	4
G82	I get emotional support from my family	0	1	2	3	4
G83	I get support from my friends	0	1	2	3	4
G84	My family has accepted my illness	0	1	2	3	4
G85	I am satisfied with family communication about my illness	0	1	2	3	4
G86	I feel close to my partner (or the person who is my main support)	0	1	2	3	4
Q1	Regardless of your current level of sexual activity, please answer the following question. If you prefer not to answer it, please mark this box  and go to the next section.					
G87	I am satisfied with my sex life	0	1	2	3	4

Please circle or mark one number per line to indicate your response as it applies to the past 7 days.

EMOTIONAL WELL-BEING

		Not at all	A little bit	Some-what	Quite a bit	Very much
GE1	I feel sad	0	1	2	3	4
GE2	I am satisfied with how I am coping with my illness	0	1	2	3	4
GE3	I am losing hope in the fight against my illness	0	1	2	3	4
GE4	I feel nervous	0	1	2	3	4
GE5	I worry about dying	0	1	2	3	4
GE6	I worry that my condition will get worse	0	1	2	3	4

FUNCTIONAL WELL-BEING

		Not at all	A little bit	Some-what	Quite a bit	Very much
GF1	I am able to work (include work at home)	0	1	2	3	4
GF2	My work (include work at home) is fulfilling	0	1	2	3	4
GF3	I am able to enjoy life	0	1	2	3	4

GF4	I have accepted my illness	0	1	2	3	4
GF5	I am sleeping well	0	1	2	3	4
GF6	I am enjoying the things I usually do for fun	0	1	2	3	4
GF7	I am content with the quality of my life right now	0	1	2	3	4

